## 7. SAFETY DEFINITIONS, REPORTING, AND MONITORING

### 7.1. Obligations of Investigator

The investigator must promptly report to the IRB/EC all unanticipated problems involving risks to patients. This includes death from any cause and all SAEs related to the use of the study drug. It is recommended that all SAEs be reported to the IRB/EC, regardless of causality.

### 7.2. Obligations of Sponsor

During the course of the study, the sponsor will report in an expedited manner all SAEs that are both unexpected and at least reasonably related to the study drug (suspected unexpected serious adverse reaction [SUSAR]), to the health authorities, IECs/IRBs as appropriate, and to the investigators (in a blinded manner).

Any AE not listed as an expected event in the Reference Safety Information section of the Investigator's Brochure or in this protocol will be considered as unexpected. Any worsening of or new onset of symptoms related to OA that occur during the screening period prior to study drug administration will be considered expected.

In addition, the sponsor will report all other SAEs that are expected and at least reasonably related to the study drug to the health authorities, according to local regulations.

At the completion of the study, the sponsor will report all safety observations made during the conduct of the trial in the clinical study report to health authorities and IECs/IRB as appropriate.

### 7.3. Definitions

#### 7.3.1. Adverse Event

An AE is any untoward medical occurrence in a patient administered a study drug which may or may not have a causal relationship with the study drug. Therefore, an AE is any unfavorable and unintended sign (including abnormal laboratory finding), symptom, or disease which is temporally associated with the use of a study drug, whether or not considered related to the study drug.

An AE also includes any worsening (ie, any clinically significant change in frequency and/or intensity) of a pre-existing condition that is temporally associated with the use of the study drug.

#### 7.3.2. Serious Adverse Event

An SAE is any untoward medical occurrence that at any dose:

- Results in **death** – includes all deaths, even those that appear to be completely unrelated to study drug (eg, a car accident in which a patient is a passenger).
- Is **life-threatening** – in the view of the investigator, the patient is at immediate risk of death at the time of the event. This does not include an AE that had it occurred in a more severe form, might have caused death.

- Requires in-patient **hospitalization** or **prolongation of existing hospitalization**. In-patient hospitalization is defined as admission to a hospital or an emergency room for longer than 24 hours. Prolongation of existing hospitalization is defined as a hospital stay that is longer than was originally anticipated for the event, or is prolonged due to the development of a new AE as determined by the investigator or treating physician.
- Results in persistent or significant **disability/incapacity** (substantial disruption of one's ability to conduct normal life functions).
- Is a **congenital anomaly/birth defect**
- Is an **important medical event** - Important medical events may not be immediately life-threatening or result in death or hospitalization, but may jeopardize the patient or may require intervention to prevent 1 of the other serious outcomes listed above (eg, intensive treatment in an emergency room or at home for allergic bronchospasm; blood dyscrasias or convulsions that do not result in hospitalization; or development of drug dependency or drug abuse).

### 7.3.3. Adverse Events of Special Interest

An AESI (serious or non-serious) is one of scientific and medical concern specific to the sponsor's product or program, for which ongoing monitoring and rapid communication by the investigator to the sponsor can be appropriate. Such an event might warrant further investigation in order to characterize and understand it. Depending on the nature of the event, rapid communication by the trial sponsor to other parties (eg, regulators) might also be warranted.

Adverse events of special interest are described in Section 7.4.3.

## 7.4. Recording and Reporting Adverse Events

### 7.4.1. Adverse Events

The investigator (or designee) will record all AEs that occur from the time the informed consent is signed until the end of the follow-up period (week 72). Refer to the study reference manual for the procedures to be followed.

Information on follow-up for AEs is provided in Section 7.4.6. Laboratory, vital signs, or ECG abnormalities are to be recorded as AEs as outlined in Section 7.4.5.

### 7.4.2. Serious Adverse Events

All SAEs, regardless of assessment of causal relationship to study drug must be reported to the sponsor (or designee) within 24 hours. Refer to the study reference manual for the procedure to be followed.

Information not available at the time of the initial report must be documented in a follow-up report. Substantiating data such as relevant hospital or medical records and diagnostic test reports may also be requested.

In the event the investigator is informed of an SAE after the patient completes the follow up period, the following will apply:

- SAE with an onset within 30 days of the end of follow-up period (week 72)/early termination visit - the SAE will be reported to the sponsor. The investigator should make every effort to obtain follow-up information on the outcome until the event is considered chronic and/or stable.
- SAE with an onset day greater than 30 days from the end of follow-up period (week 72)/early termination visit - only SAEs deemed by the investigator to be drug-related SAEs will be reported to the sponsor. The investigator should make every effort to obtain follow-up information on the outcome of a drug-related SAE until the event is considered chronic and/or stable.
- SAE reported by the patient at the end of study phone call and deemed by the investigator to be drug related will be reported to the sponsor. The investigator should make every effort to obtain follow-up information on the outcome of a drug-related SAE until the event is considered chronic and/or stable.

#### 7.4.3. Other Events that Require Accelerated Reporting

The following events also require reporting to the sponsor (or designee) within 24 hours of learning of the event:

**Symptomatic Overdose of Study Drug:** Accidental or intentional overdose of at least 2 times the intended dose of study drug within the intended therapeutic window, if associated with an AE,

**Pregnancy:** Although pregnancy is not considered an AE, it is the responsibility of the investigator to report to the sponsor (or designee), by telephone within 24 hours of identification, any pregnancy occurring in a female patient during the study or within 20 weeks of the last dose of study drug. Any complication of pregnancy affecting a female study patient and/or fetus and/or newborn must be reported as an SAE. Outcome for all pregnancies should be reported to the sponsor.

**Adverse Events of Special Interest:** All AESI, serious and non-serious, must be reported within 24 hours of identification using the same reporting process as for SAE reporting, per Section 7.4.2. Monitoring of AESIs is described in Section 7.6. Events considered to be AESIs are:

- Adjudicated arthropathy (as confirmed by adjudication)
- Sympathetic nervous system dysfunction (as diagnosed after consultation with an appropriate specialist, such as a neurologist and/or cardiologist)
- Peripheral sensory AEs that require a neurology or other specialty consultation
- JR surgery (refer to Section 7.6.1.4 for when to report as an AESI)
  - Patients should be counselled that if they require JR surgery during the trial, they should contact the site immediately and have pre-operative X-rays and MRI

completed of the joint that will be replaced. The pre-operative images must be submitted to the central imaging vendor for adjudication

#### **7.4.4. Reporting Adverse Events Leading to Withdrawal from the Study**

All AEs that lead to a patient's withdrawal from the study must be reported to the sponsor's medical monitor within 30 days.

Refer to the study reference manual for the procedures to be followed.

#### **7.4.5. Abnormal Laboratory, Vital Signs, or Electrocardiogram Results**

The criteria for determining whether an abnormal objective test finding should be reported as an AE include:

- the test result is associated with accompanying symptoms, and/or
- the test result requires additional diagnostic testing or medical/surgical intervention, and/or
- the test result leads to a change in dosing (outside of protocol-stipulated dose adjustments), discontinuation from the study, significant additional concomitant drug treatment, or other therapy

Contact the medical monitor in the event the investigator feels that an abnormal test finding should be reported as an AE, although it does not meet any of the above criteria.

Repeating an abnormal test, in the absence of any of the above conditions, does not constitute an AE. Any abnormal test result that is determined to be an error does not require reporting as an AE.

Evaluation of severity of laboratory abnormalities will be assessed according to the scale outlined in Section 7.5.1.

#### **7.4.6. Follow-up**

Adverse event information will be collected until the patient's last study visit.

Serious adverse event information will be collected until the event is considered chronic and/or stable.

### **7.5. Evaluation of Severity and Causality**

#### **7.5.1. Evaluation of Severity**

Adverse events will be graded according to the following scale:

- **Mild:** Does not interfere in a significant manner with the subject's normal functioning level. It may be an annoyance. Prescription drugs are not ordinarily needed for relief of symptoms, but may be given because of personality of the subject.
- **Moderate:** Produces some impairment of functioning but is not hazardous to health. It is uncomfortable or an embarrassment. Treatment for symptom may be needed.

- **Severe:** Produces significant impairment of functioning or incapacitation and is a definite hazard to the subject's health. Treatment for symptom may be given and/or subject hospitalized.

### 7.5.2. Evaluation of Causality

#### Relationship of AEs to Study Drug:

The relationship of AEs to study drug will be assessed by the blinded investigator, and will be a clinical decision based on all available information. The following question will be addressed:

Is there a reasonable possibility that the adverse event may have been caused by the study drug?

The possible answers are:

**Not Related:** There is no reasonable possibility that the event may have been caused by the study drug

**Related:** There is a reasonable possibility that the event may have been caused by the study drug

The investigator should justify the causality assessment of each SAE.

A list of factors to consider when assessing the relationship of AEs to study drug is provided below. Please note that this list is not exhaustive.

Is there a reasonable possibility that the event may have been caused by the study drug?

No:

- due to external causes such as environmental factors or other treatment(s) being administered
- due to the patient's disease state or clinical condition
- do not follow a reasonable temporal sequence following the time of administration of the dose of study drug
- do not reappear or worsen when dosing with study drug is resumed

Yes:

- could not be explained by environmental factors or other treatment(s) being administered
- could not be explained by the patient's disease state or clinical condition
- follow a reasonable temporal sequence following the time of administration of the dose of study drug
- resolve or improve after discontinuation of study drug
- reappear or worsen when dosing with study drug
- are known or suspected to be a response to the study drug based upon preclinical data or prior clinical data

**Relationship of AEs to Study Conduct:**

The relationship of AEs to study conduct will be assessed by the blinded investigator, and will be a clinical decision based on all available information. The following question will be addressed:

Is there a reasonable possibility that the adverse event may have been caused by study conduct?

The possible answers are:

**Not Related:** There is no reasonable possibility that the event may have been caused by study conduct

**Related:** There is a reasonable possibility that the event may have been caused by study conduct

The investigator should justify the causality assessment of each SAE.

A list of factors to consider when assessing the relationship of AEs to study drug is provided below. Please note that this list is not exhaustive.

Is there a reasonable possibility that the event may have been caused by the study conduct?

No:

- due to external causes such as environmental factors or other treatment(s) being administered
- due to the patient's disease state or clinical condition
- do not follow a reasonable temporal sequence following the course of the study.
- do not reappear or worsen when dosing with study participation is resumed

Yes:

- could not be explained by environmental factors or other treatment(s) being administered
- could not be explained by the patient's disease state or clinical condition
- follow a reasonable temporal sequence following the course of the study.
- resolve or improve after discontinuation from study participation.
- reappear or worsen when study participation is resumed

**7.6. Safety Monitoring**

The investigator will monitor the safety of study patients at his/her site(s) as per the requirements of this protocol and consistent with current Good Clinical Practice (GCP). Any questions or concerns should be discussed with the sponsor in a timely fashion. The sponsor will monitor the safety data from across all study sites. The medical monitor will have primary responsibility for the emerging safety profile of the compound. The study monitor will be supported by other departments (eg, Pharmacovigilance and Risk Management; Biostatistics and Data Management). Safety monitoring will be performed on an ongoing basis (eg, individual review of SAEs) and on a periodic cumulative aggregate basis.

## 7.6.1. Monitoring Adverse Events of Special Interest

### 7.6.1.1. Adjudicated Arthropathy

Adjudicated arthropathy is an umbrella term that encompasses the following conditions:

- Rapidly progressive OA type 1 and 2
- Subchondral insufficiency fractures
- Primary osteonecrosis

In addition, adjudicated arthropathies will be evaluated to determine if they meet the criteria for destructive arthropathy.

Potential events of adjudicated arthropathy will be monitored via clinical signs and symptoms of worsening joint pain (joint pain questionnaire), AE monitoring, and routine imaging.

Clinically significant worsening of joint pain during the course of this study is defined as worsening of pain in any joint despite treatment with analgesics (see Section 5.2), which is inconsistent with the normal progression of OA and that lasts at least 2 weeks (or less at the discretion of the investigator).

If a patient reports an increase in joint pain, as described above, then study drug administration will be withheld. Imaging of the affected joint will be performed, as well as any additional imaging deemed appropriate to understand the cause of the worsening pain (Section 6.3.4.8). The decision to perform imaging after patient reports of worsening joint pain will be documented in the respective CRF page. Images, along with any other radiographic evaluation, will be submitted to the Adjudication Committee for review (Section 3.4). The investigator may consider aspiration of synovial fluid for further analysis such as cell count and crystal analysis.

If routine imaging suggests one of the forms of adjudicated arthropathy, then study drug administration will be withheld. Any additional imaging deemed appropriate will be obtained. Images, along with any other radiographic evaluation, will be submitted to the Adjudication Committee for review (Section 3.4).

If the adjudication does not confirm the case as adjudicated arthropathy according to the adjudication criteria, study drug may be restarted.

Patients with findings that suggest adjudicated arthropathy will have their dosing terminated and will be referred for orthopedic consultation, and once confirmed by the adjudication committee, the case must be reported as an AESI (Section 7.3.3 and Section 7.4.3).

Patients should be encouraged to return to the clinic for remaining study visits. Prior to the scheduled JR, the patient should complete the pre-operative study visit and week 4 and week 20 post-operative study visits (Section 6.2.11 and Section 6.3.4.10). Pre-operative images, along with any other radiographic evaluation will be submitted to the Adjudication Committee for review (Section 3.4).

Details of data collection for adjudication of events will be provided in the adjudication charter.

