Safety assessments will be performed at each study visit during treatment period 1, as outlined in [Table 1](#). Potential events of adjudicated arthropathy will be monitored via clinical signs and symptoms of worsening joint pain during the study (eg, using the joint pain questionnaire and imaging). Potential events of sympathetic nervous system dysfunction will be monitored throughout the study through physical examination, AE reporting, assessment of orthostatic hypotension and via the Survey of Autonomic Symptoms.

Efficacy assessments will be performed for patients participating in the sub-study as outlined in [Table 3](#). Sub-study patients should discontinue use of paracetamol/acetaminophen 24 hours prior to the start of study visits during treatment period 1 in order to minimize the confounding effects of the rescue medication on efficacy measurements.

- **Treatment Period 2 (starts with study drug administration at week 16 and continues through week 52):** Treatment period 2 begins at the week 16 visit and continues through the week 52 visit. Patients will continue to receive fasinumab 1 mg Q8W, 1 mg Q4W or placebo Q4W during this period. At the week 24 visit, X-rays of the hips, knees, and shoulders will be obtained. The last dose of study drug will be administered at week 48.

During treatment period 2, patients may use non-NSAID standard-of-care pain treatment as rescue treatment and limited use of oral NSAIDs for non-OA related pain or fever.

Non-steroidal anti-inflammatory drugs will be study-provided as tablets or capsules, and may be used for up to 10 days in an 8-week period, 30 days in a 6-month period, and 60 days in a 1-year period. Use of oral NSAIDs in excess of these amounts is prohibited. The daily dose should not exceed the recommended maximum daily dose per the product labeling. Topical NSAIDs are prohibited during treatment period 2. Patients may be withdrawn from the study after appropriate counseling if continued noncompliance with protocol-defined maximum NSAID use occurs.

Patients will continue to be supplied with paracetamol/acetaminophen during treatment period 2.

The use of paracetamol/acetaminophen and/or NSAIDs should be recorded daily by the patient in the patient's diary. All other pain medications will be obtained and used per local standard-of-care; their use will be reported as concomitant medication during regular study visits.

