##### **5.3.2.1. Reasons for Permanent Discontinuation of Study Drug**

Study drug dosing will be permanently stopped in the event of:

- A patient being randomized under amendment 3 or a subsequent amendment and treated with the 3 mg Q4W or 6 mg Q8W dosing regimen
- A patient being randomized under an earlier version of the protocol before amendment 3 and treated with the 6 mg Q4W, 9 mg Q4W, or placebo Q4W dosing regimen
- A subject developing clinically significant sensory and motor neurologic events confirmed by a neurologist's examination and graded by the neurologist as at least

moderate peripheral neuropathy limiting activities of daily living, ie, grade  $\geq 2$  according to v.4 (CTCAE); study sites should use CTCAE v.4 criteria throughout the study for consistency

- Evidence of pregnancy
- A patient developing new or worsening signs and symptoms indicative of carpal tunnel syndrome
- Continued noncompliance with protocol-defined maximum NSAID use (see Section 4.3) after appropriate counseling
- Continued noncompliance with protocol-defined maximum acetaminophen/paracetamol use (with a maximum daily dose of 2500 mg in Europe and other countries where 500 mg strength tablets/capsules are available and 2600 mg in any countries outside of Europe where 325 mg strength tablets/capsules are available) after appropriate counseling
- JR Surgery
- AESI:
  - Adjudicated arthropathy, as described in Section 7.6.1.1
  - Sympathetic nervous system dysfunction, as described in Section 7.6.1.2
- Hepatotoxicity
  - Study drug should be discontinued if:
    - a) Total bilirubin (TBL)  $>2x$  ULN or international normalized ratio (INR)  $>1.5$  and
    - b) Alanine aminotransferase (ALT) or aspartate aminotransferase (AST)  $>3x$  ULN and
    - c) No other cause for a and b is readily apparent

Other causes of ALT, AST, and TBL elevations can include alcoholic hepatitis, autoimmune hepatitis, non-alcoholic hepatitis, heritable diseases (Gilbert's Syndrome), heart failure, and viral hepatitis.

Study drug may be withheld in patients who do not meet criteria for permanently discontinuing study drug, until an alternative cause for drug-induced liver injury can be determined. The patient may be re-challenged if an alternative cause for elevated liver function tests is found and the liver function tests return to baseline, but only after discussion with the sponsor.

- Systemic hypersensitivity reaction assessed as related to study medication

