### **5.3.2.2. Reasons for Temporary Discontinuation of Study Drug**

Study drug may be temporarily discontinued due to medical need, as determined by the investigator. Study drug will be temporarily withheld while awaiting imaging adjudication for worsening joint pain or when routine imaging suggests adjudicated arthropathy and prompts the need for additional imaging (Section 7.6.1.1), or for patients who are determined to have orthostatic hypotension or determined to have new or worsening symptoms suggestive of sympathetic nervous system dysfunction while awaiting evaluation by a specialist (Section 7.6.1.2). Study drug should not be re-started until the next study visit unless imaging/evaluation results are available within the current visit window.

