### 7.6.1.2. Sympathetic Nervous System Dysfunction

Sympathetic nervous system dysfunction will be monitored throughout the study through physical examination, AE reporting, assessment of orthostatic hypotension, and the Survey of Autonomic Symptoms (Section 6.3.4.5). New onset or worsening of signs and symptoms of autonomic dysfunction will be evaluated by the investigator. Sympathetic nervous system dysfunction will only be diagnosed after consultation with an appropriate specialist, such as a neurologist and/or cardiologist.

In cases where new or worsening symptoms consistent with sympathetic nervous system dysfunction are moderate to severe or are clinically significant and do not resolve or return to baseline in 2 weeks (or less at the discretion of the investigator), study drug will be withheld and the patient will be referred to a specialist. If the evaluation by the appropriate specialist does not suggest sympathetic nervous system dysfunction, study drug may be restarted. If the specialist's evaluation does reveal sympathetic nervous system dysfunction then study drug will be permanently discontinued and the case reported as an AESI (Section 7.4.3).

Orthostatic hypotension may be a manifestation of sympathetic nervous system dysfunction. If a patient is determined to have orthostatic hypotension, study drug should be withheld and the AE should be entered in the eCRF. The following procedures should be followed:

- If the patient is symptomatic and a clinical explanation for orthostatic hypotension is identified (such as a new medication or dehydration due to exercise or illness or excessive heat exposure), study drug will be withheld, and the patient should return to the study site for an unscheduled visit in 1 to 10 days for an unscheduled assessment of orthostatic hypotension. If the orthostatic hypotension has resolved, study drug may be restarted. If the orthostatic hypotension has not resolved, then study drug will be withheld, and the patient will be referred to a specialist (neurologist or a cardiologist) for evaluation of sympathetic nervous system dysfunction.

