5.1.7. Analysis of Safety Data

The analysis of safety and tolerability will be performed on the SAF-LTS, as defined in Section 3.2.

The safety analysis will be based on the reported AEs and other safety information (clinical laboratory evaluations, vital signs, 12-lead ECG, Physical Examination, etc.).

Treatment-Emergent Potential Clinically Significant Values (PCSV) in laboratory variables, vital signs and ECG are defined in [Appendix 11.2](#).

Period of observation: The observation period will be divided into three segments: pre-treatment, on-treatment and post-treatment.

- The pre-treatment period is defined as the time between when the patients give informed consent and the start of study drug.
- The LTS on-treatment period is defined as the time from first dose of study drug up to 28 days after the last dose of study drug. The LTS post-treatment period is defined as the time starting 29 days after last dose of study drug (after the on-treatment period) to up to 24 weeks post the last dose of study drug (up to week 72).

Day 1 is the first day of study drug, Day -1 is the day before Day 1, and there is no Day 0.

The time interval to detect any on-treatment event or abnormality is between the first dose of double-blind study drug injection and the end of treatment plus 28 days. Data collected outside this interval will be excluded from the estimation of descriptive statistics and identification of abnormalities for laboratory evaluations, ECGs and vital signs. All post-baseline data during the interval will be using in the PCSV analysis including scheduled and unscheduled assessments.

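### Protocol 7.6.1.1 ends dosing for findings that only suggest adjudicated arthropathy, although the same section lets study drug restart if adjudication does not confirm it

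*Protocol*

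**What the plan says.** Protocol Section 7.6.1.1 sets out what happens when AA is suspected. If routine imaging points to one of its forms, study drug is withheld and the images go to the Adjudication Committee. Then: "If the adjudication does not confirm the case as adjudicated arthropathy according to the adjudication criteria, study drug may be restarted". The next paragraph reads: "Patients with findings that suggest adjudicated arthropathy will have their dosing terminated". That sentence goes on to require orthopedic referral and, once the committee has confirmed the case, reporting as an adverse event of special interest (AESI).

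Three other places in the protocol bear on the same decision:

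- Section 5.3.2.2, temporary discontinuation: "Study drug will be temporarily withheld while awaiting imaging adjudication for worsening joint pain or when routine imaging suggests adjudicated arthropathy".
- Section 5.3.2.1, permanent discontinuation, under the AESI heading: "Adjudicated arthropathy, as described in Section 7.6.1.1".
- Section 7.4.3, which defines the AESI: "Adjudicated arthropathy (as confirmed by adjudication").

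On the analysis side, SAP Section 5.1.7 states: "The LTS on-treatment period is defined as the time from first dose of study drug up to 28 days after the last dose". Exposure is the last dose date minus the first dose date, plus 28 days (Protocol 9.5.3.3, SAP 5.1.6.2).

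**The concern.** One trigger, findings that suggest AA, has two consequences. The first is a hold that can be lifted. The second is an end to dosing, in a sentence where confirmation applies only to AESI reporting. Both cannot apply to a patient whose images look suspicious and who is then cleared.

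A site that looks up the permanent-stop rule in 5.3.2.1 finds no criterion there, only a reference to 7.6.1.1, and so arrives at the conflicting sentence. One site could restart a cleared patient while another stops the same kind of patient for good. What is at stake is treatment status, exposure, the on-treatment window and discontinuation counts for suggestive but unconfirmed cases among patients still being dosed. AA is a central risk in this safety study, so its stopping rule should read the same way everywhere.

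**Working it through.** **Which sentence is wrong**

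| Source (Protocol) | Trigger | Action |
|---|---|---|
| 7.6.1.1, routine-imaging paragraph | imaging suggests AA | withhold, adjudicate |
| 7.6.1.1, next paragraph | not confirmed | may restart |
| 7.6.1.1, termination sentence | findings suggest AA | dosing terminated |
| 5.3.2.2 | imaging suggests AA, adjudication pending | temporary hold |
| 5.3.2.1 with 7.4.3 | AA as an AESI, that is, confirmed | permanent stop |

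Only the termination sentence ties an end of dosing to suspicion. The rule for sympathetic nervous system dysfunction in 7.6.1.2 follows the same hold, evaluate, then restart-or-stop pattern: "If the evaluation by the appropriate specialist does not suggest sympathetic nervous system dysfunction, study drug may be restarted".

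**What one case costs**

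Inputs:

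- Injections are given every 4 weeks from day 1 to week 48 (Protocol 5.1), so 48/4 + 1 = 13 are planned.
- The study day of week w is 7w + 1.
- Exposure = last dose day − first dose day + 28.
- The on-treatment window ends at last dose day + 28.
- Scheduled radiographs: "At the week 24 visit, X-rays of the hips, knees, and shoulders will be obtained" (Protocol 3.1). The next are at week 52 (Protocol Table 2), after the last dose. Week 24 is therefore the only scheduled on-treatment radiograph with doses still to come.

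Assumption: the patient is cleared, restarts at the next visit (Protocol 5.3.2.2) and then completes dosing.

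| Week 24 flag | Last dose | Exposure (days) | Window ends | Injections |
|---|---|---|---|---|
| Hold and restart | week 48, day 337 | 336 + 28 = 364 | day 365 | 12 |
| Terminate, week 24 dose withheld | week 20, day 141 | 140 + 28 = 168 | day 169 | 6 |
| Terminate, week 24 dose given before the read, week 28 withheld | week 24, day 169 | 168 + 28 = 196 | day 197 | 7 |

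Differences from hold and restart:

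- Week 24 dose withheld: 364 − 168 = 196 days (54% of 364) and 12 − 6 = 6 injections.
- Week 28 dose withheld: 364 − 196 = 168 days (46%) and 12 − 7 = 5 injections.

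The on-treatment window shortens by the same 168 to 196 days. New adverse events in that time count as post-treatment rather than treatment-emergent.

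For imaging triggered by pain, the gap depends on which dose is withheld:

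- Week 4 dose: 364 − 28 = 336 days.
- Week 44 dose: last dose at week 40, exposure 280 + 28 = 308, gap 56 days.
- Week 48 dose: no later dosing visit, so both readings agree and the gap is 0.

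The number of suggestive but unconfirmed cases is not in the documents, so these per-case figures cannot be scaled to the trial.

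**The case against.** The strongest reply is that the section can be read in sequence: withhold, adjudicate, restart if not confirmed, and terminate the rest. Coming straight after the not-confirmed exception, the termination sentence would then cover confirmed cases only. The following text, on remaining visits and scheduled joint replacement, suits patients with real joint disease. This is probably what was meant, but it is not what is written. The trigger is findings that suggest AA, confirmation is attached only to reporting, and the section uses a different word, withheld, for the interim step.

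Several other points stand and limit the impact:

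- Restart is permissive, and 5.3.2.1 also allows a permanent stop for medical need or by sponsor or patient decision. Sites could still differ after the fix.
- Events that leave the treatment-emergent window are not lost. SAP 5.1.8.1 summarizes post-treatment events in the same way.
- The incidence-rate models in SAP 5.1.7.1 use observation days, not exposure, as the offset, and patients who stop drug are asked to attend all remaining visits. A cleared patient is not an AA event on either reading.
- Some lost injections are placebo: alternate ones in the 1 mg Q8W arm and all of them in the placebo arm.
- The sympathetic-dysfunction rule is an analogy and does not prove the intent for AA.

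None of this removes the contradiction from a dosing rule that sites have to follow.

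**Conclusion.** The concern holds. The termination sentence in Protocol 7.6.1.1 contradicts the restart sentence before it and the temporary-hold rule in 5.3.2.2, and the permanent-stop bullet in 5.3.2.1 points to it. It should be corrected.

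The size is per case. A cleared patient flagged at week 24 loses 168 to 196 of 364 days of exposure and 5 to 6 injections under the termination reading. For pain-triggered imaging the loss runs from 336 days down to 0. These figures assume that the patient would have restarted at the next visit and completed dosing. No trial-level effect is claimed. Because dosing stops on suspicion under either reading, no patient is dosed while AA is suspected. Sample size, power and alpha are unaffected.

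**What to change.** Replace the termination sentence in Protocol 7.6.1.1 with wording such as:

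> When findings suggest adjudicated arthropathy, study drug is withheld and the patient is referred for orthopedic consultation. If the adjudication committee confirms the diagnosis, study drug is permanently discontinued and the event is reported as an AESI.

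In 5.3.2.1, change the bullet to: *Adjudicated arthropathy confirmed by the adjudication committee (see Section 7.6.1.1)*.

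This keeps the immediate hold and the referral, and ties the permanent stop to confirmation. If the sponsor did intend to stop for good on suspicion, then the restart sentence and 5.3.2.2 are the ones to change.

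The cost is one sentence and one bullet, with no change to the case report form, SAP, sample size or analysis. The edit has to go through an IRB/EC-approved amendment under Protocol Section 14, with competent-authority approval if it is classed as substantial. It could be carried with other clarifications, as Amendment 9 did.
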